1.0 SYNOPSIS

Study Title:	An Open-label Study Evaluating the Long-term Efficacy, Quality of Life, and Safety of ABSORICA® (isotretinoin) Capsules Administered Without Food in Patients With Severe Recalcitrant Nodular Acne
Protocol Number:	ABS1517LT
Sponsor:	RANBAXY LABORATORIES Inc [name]
Development Phase:	4
Study Objectives:	
20-Week Active Treatment Period (ATP) The primary objective during the 20-week ATP of the study will be to investigate the quality of life (QOL) of subjects who are taking Absorica® (isotretinoin) capsules twice daily (bid) without food for the treatment of severe recalcitrant nodular acne.
 
The secondary objective during the 20-week treatment period will be to investigate the efficacy and safety of Absorica® (isotretinoin) taken bid without food during the ATP.
 
104-Week Post-treatment Period (PTP) The primary objective during the 104-week PTP of the study is to determine both the time to retreatment and the proportion of subjects who require retreatment with oral isotretinoin during a 2-year PTP.
 
The secondary objectives during the PTP are:
 
 • To investigate the QOL at the end of the 2-year PTP; • To investigate the severity of the acne over time, as measured by the Investigator's Global Assessment (IGA) and lesion counts; • To document any acne treatment (prescription and/or over-the-counter [OTC]) used by those subjects; • To evaluate the long-term safety during the 2-year PTP.
Study Design:	Uncontrolled open-label.
Planned Sample Size:	200 enrolled subjects
Study Population:	Eligible subjects will include healthy males and non-pregnant, non-nursing females, age 12 to 45 years, with severe recalcitrant nodular acne.
Investigational Product(s):	ABSORICA® (isotretinoin) capsules 0.5 mg/kg/day for 4 weeks followed by 1.0 mg/kg/day for 16 weeks. Female subjects must consent to 2 forms of birth control or abstinence.
Reference Product(s):	Not applicable
Control Product(s):	Not applicable
Evaluation Criteria:	
The primary endpoint during the ATP will be the change from Baseline to the end of ATP (Week 20/Visit 8) in the acne-specific quality of life (acne-QOL) questionnaire score for those subjects who complete the 20-week ATP and are at least 75% compliant with the treatment regimen.
 
Secondary endpoints for the ATP will be:
 
 • The change from Baseline in the lesion count (nodules and inflammatory lesions) at the end of the ATP;

	
 • The change from Baseline in the acne-QOL score at Weeks 4, 8, 12, and 16 weeks; • The change from Baseline in the IGA at the end of the ATP in subjects who complete the 20-week ATP; • Treatment safety, as determined by the frequency and severity of adverse events (AEs) and local skin irritation. 
Primary endpoints for the PTP will be to determine:
 
 • The proportion of subjects who require retreatment with oral isotretinoin at any time during the PTP; and • The time at which retreatment is required. 
Secondary endpoints for the PTP will be to determine:
 
 • The proportion of subjects who require treatment with a prescription anti-acne medication other than oral isotretinoin at any time during the PTP; • The proportion of subjects who use an over-the-counter (OTC) anti-acne medication at any time during the PTP; • The severity of acne (lesion count and IGA) at the time of retreatment in subjects treated with a prescription or OTC anti-acne treatment; • The severity of acne (lesion count and IGA) at each visit; • The time to retreatment with a prescription or over-the-counter (OTC) anti-acne medication at any time during the PTP; • The acne-QOL at the end of the PTP; • Safety as assessed through the monitoring of AEs, laboratory test results, vital signs, and physical examinations.
Pharmacokinetics Evaluation Criteria:	Not applicable
Safety Evaluation Criteria:	During the ATP: adverse event (AE) incidence and severity, laboratory test results (hematology, serum biochemistry, lipid profile), pregnancy tests, vital signs (systolic and diastolic blood pressure, heart rate, respiratory rate) During the PTP: Serious AEs related to study drug.
Statistical Methods:	Efficacy will be evaluated descriptively. Adverse events will be presented in data listings and summarized by frequency and severity. Laboratory and vital sign data will be presented in data listings. Abnormal laboratory findings will be presented. Results from the acne-QOL will be summarized.
Study Sites:	Approximately 20 study sites in the United States (US)
Planned Dates of Study:	January 2015 – April 2018

Table 1-1 Visit Schedule and Assessments – Active Treatment Phase (ATP)

	Visit 1	Visit 2	Visit 3	Visit 4	Visit 5	Visit 6	Visit 7	Visit 8 EOT
	Screening ≤30 days of Baseline ^a	Baseline	Week 2 ± 4 days	Week 4 ± 4 days	Week 8 ± 4 days	Week 12 ± 4 days	Week 16 ± 4 days	Week 20 ± 4 days
		0.5 mg/kg/day						1.0 mg/kg/day
Informed consent ^b including photographic consent	X							
Inclusion/exclusion criteria	X	X						
Demographics and medical history	X							
Physical examination	X							X
Vital signs and weight	X							X
Prior and concomitant medication assessment	X	X	X	X	X	X	X	
Childbearing potential (female subjects only) ^c	X	X						
Clinical laboratory assessment ^d	X	X	X	X	X	X	X	
Hematology								
Serum chemistry								
Pregnancy test ^e	X	X	X	X	X	X	X	X
Contraceptive counseling	X	X		X	X	X	X	X
Photography ^f		X		X	X	X	X	X
Quality of Life Questionnaire		X		X	X	X	X	X
Investigator's Global Assessment (IGA)		X		X	X	X	X	X
Lesion count ^g (nodules and inflammatory lesions)	X	X		X	X	X	X	X
Adverse event assessment		X	X	X	X	X	X	X
Issue 30-day supply of study medication		X	X	X	X	X	X	
Reconcile medication use and counsel as required			X	X	X	X	X	X

EOT = end of treatment

^a Females of childbearing potential must undergo a mandatory 30-day waiting period before receiving isotretinoin.^b Subjects under 18 years of age must sign and assent to participate in the study as well as have written informed consent from a parent or guardian. The parent or guardian must also give permission for a minor to receive contraceptive counseling.

- c. Childbearing potential includes dates of menstruation and forms of contraceptives currently used and to be used during the study.
- d. Laboratory assessments at Screening and EOT will include a complete blood count, fasting clinical chemistry, and fasting lipid profile. Laboratory assessments at all other visits will include only fasting clinical chemistry and fasting lipid profile.
- e. Females of childbearing potential must have a second, confirmatory pregnancy test with negative results that occurs after the 30-day waiting period.
- f. Specified sites will perform photography using equipment supplied by the photography vendor; other sites will use on-site photography equipment.
- g. Only nodules will be counted at Screening.

Table 1-2 Visit Schedule and Assessments – Post-Treatment Phase (PTP)

	Visit 9	Visit 10	Visit 11	Visit 12	Visit 13	Visit 14/EOS
	Week 24 ± 4 days	Week 32 ± 2 weeks	Week 46 ± 2 weeks	Week 72 ± 2 weeks	Week 98 ± 2 weeks	Week 124 ± 2 weeks
Vital signs and weight	X					
Clinical laboratory assessment ^a	X					
Serum chemistry						
Pregnancy test	X					
Prior and concomitant medication assessment	X	X	X	X	X	X
Photography ^b		X	X	X	X	X
Quality of Life Questionnaire		X	X	X	X	X
Investigator's Global Assessment (IGA)		X	X	X	X	X
Lesion count (nodules and inflammatory lesions)		X	X	X	X	X
Adverse event assessment ^c	X	X	X	X	X	X

a. Laboratory assessments at Visit 9 will include fasting clinical chemistry and fasting lipid profile.

b. Specified sites will perform photography using equipment supplied by the photography vendor; other sites will use on-site photography equipment.

c. Only serious adverse events related to study treatment will be collected.

TABLE OF CONTENTS

1.0	SYNOPSIS	2
TABLE OF CONTENTS		7
LIST OF TABLES		11
LIST OF FIGURES		11
LIST OF ABBREVIATIONS AND DEFINITION OF TERMS		12
2.0	INTRODUCTION	14
2.1	Background	14
2.2	Rationale of the Study	15
2.3	Benefit-Risk Assessment	15
3.0	TRIAL OBJECTIVES AND PURPOSE	16
3.1	20-Week Active Treatment Period (ATP)	16
3.2	104-Week Post-Treatment Period (PTP)	17
4.0	STUDY DESIGN	17
4.1	Overall Study Design	17
4.2	Study Endpoints	18
4.2.1	Active Treatment Period	18
4.2.1.1	Primary Endpoint for the ATP	18
4.2.1.2	Secondary Endpoints for the ATP	19
4.2.2	Post-Treatment Period	19
4.2.2.1	Primary Endpoints for the PTP	19
4.2.2.2	Secondary Endpoints for the PTP	19
5.0	SELECTION OF STUDY POPULATION	20
5.1	Subject Population	20
5.2	Inclusion Criteria	20
5.2.1	General Inclusion Criteria	20
5.2.2	Specific Inclusion Criteria	20
5.3	Exclusion Criteria	21
5.3.1	General Exclusion Criteria	21
5.3.2	Female Specific Exclusion Criteria	21
5.3.3	Concurrent Disease Exclusion Criteria	22
5.3.4	Hypersensitivity/Allergy Exclusion Criteria	22
5.3.5	Prohibited Medication Before and/or During the Study	22

SAP	Statistical Analysis Plan

Abbreviation	Definition
SAR	Suspected adverse reaction
SCID-CT	Structured Clinical Interview DSM-IV clinical trials
SOP	Standard operating procedure
SUSAR	Suspected unexpected serious adverse reaction
UPT	Urine pregnancy test
US	United States
WBC	White blood cell

2.0 INTRODUCTION

2.1 Background

Acne is a common skin condition, affecting a large portion of the general population, particularly adolescents. The prevalence of acne amongst adolescents is estimated between 70% and 87%,¹ with approximately 95% to 100% of boys and 83% to 85% of girls aged 16 to 17 years² affected by this condition. Cystic acne is estimated to affect approximately 17 million people in the United States (US), which includes 80% of all persons between the ages of 11 and 30 years, regardless of race, ethnicity, or gender.³

Acne lesions occur primarily on the face, neck, upper back, and chest. Noninflammatory lesions include open or closed comedones (blackheads and whiteheads, respectively). Inflammatory lesions include papules, pustules, and nodules/nodular cystic lesions, with the type of inflammatory lesions depending on the severity and location of the inflammation within the dermis. Nodules are defined as inflammatory lesions that are greater than 5 mm in diameter. Severe nodular acne, defined as grade 4 or 5 acne on the Investigator's Global Assessment (IGA) scale, is a skin condition characterized by intense erythema, inflammation, nodules, cysts, and scarring. Variants of nodular acne include acne conglobata, acne fulminans, and pyoderma faciale.

Acne can have an important and potentially lasting impact on quality of life and self-image, especially during the emotionally critical period of adolescence. Persons with acne may think of themselves as unworthy and socially unacceptable. Severe acne may lead to scarring and disfigurement, aggravating the already present psychosocial aspects of this condition. Acne also has a significant economic and social impact on doctor visits, medications, and absenteeism.³ Patients with acne report levels of social, psychological, and emotional problems as great as those reported by patients with chronic disabling asthma, epilepsy, diabetes, back pain, or arthritis.⁴

Isotretinoin (13-cis-retinoic acid) is an oral retinoid that has been approved in the US since 1982 for patients with recalcitrant, severe nodular or scarring acne, acne conglobata, and acne fulminans.⁵ Isotretinoin has also been used off-label as an effective treatment of acne that is either treatment-resistant or is producing physical or psychological scarring. Isotretinoin is the only agent that targets all pathophysiological processes of acne; it reduces the secretion of sebum, decreases the size of the sebaceous glands, prevents the development of comedones, and decreases the colonization with *Propionibacterium acnes* (*P. acnes*), the prevalent bacterium in acne. It also possesses anti-inflammatory properties, and reduces the levels of metalloproteinases in sebum.^{3,5} The approved dosage of 0.5 to 1.0 mg/kg/day⁶ is typically given over a 20-week course, to a total cumulative dose of 120 to 150 mg/kg.^{4,5,7} Beyond this maximal dosing, no further benefit has been reported. However, if this dosage range has not been achieved, patients

are more likely to relapse and require subsequent courses of therapy.⁵ Patients often require only a single course of treatment with isotretinoin and improvement continues even after the drug has been stopped.³

In one study, 69% of patients (61/88) were still virtually clear of disease an average of 9 years after completing treatment with isotretinoin, whereas of the remaining patients, 16% required further treatment with conventional antibiotics and 23% required a second course of isotretinoin.⁸ Relapses have been reported to occur in approximately 23% of patients (primarily during the first 2 years after treatment discontinuation) even in patients who received a full course of 150 mg/kg of isotretinoin.⁹ Recent studies examining risk factors for relapse in patients treated with isotretinoin emphasize the importance of the total cumulative dose rather than the daily dose used during treatment. Patients treated with a lower cumulative dose (less than 120 mg/kg) have a significantly higher recurrence rate than patients treated with a higher cumulative dose.⁴ One study found a significant association between acne relapse and the following factors: male gender, age under 16 years, living in an urban area, isotretinoin cumulative doses above 2,450 mg, and isotretinoin treatment longer than 121 days.¹⁰

The current study will be conducted to evaluate the safety and efficacy of Absorica® (isotretinoin), a modified formulation of isotretinoin. Although isotretinoin is the most effective drug for the treatment of severe recalcitrant nodular acne, the molecule is quite lipophilic. Because of this lipophilicity, isotretinoin products such as Amnesteem® and Claravis®, etc.¹¹⁻¹⁵ must be taken with a high-fat meal to achieve optimal absorption. When these formulations are administered without food, fasted plasma levels of the active drug can be nearly 60% lower than fed levels. Noncompliance with the food intake results in large fluctuations in drug plasma levels (up to approximately three times between fasting and fed conditions) and can compromise the efficacy of isotretinoin. Absorica® (isotretinoin) has been developed as a formulation for which absorption is less dependent on the amount and/or type of food intake, thus providing a more reliable isotretinoin blood concentration.

2.2 Rationale of the Study

Previous studies with isotretinoin products, including Absorica® (isotretinoin), have been performed with the subject in a fed state. This study is designed to provide efficacy, safety, and quality of life (QOL) data on subjects who receive Absorica® without food. The study will investigate the efficacy of the treatment, the frequency of relapse once the treatment has been discontinued, the quality of life during the active treatment and during a 2-year period after treatment has been completed, and the overall safety of treatment with Absorica®.

2.3 Benefit-Risk Assessment

Isotretinoin is currently regarded as the most effective treatment option for severe nodular or nodular cystic acne, due to the ability of this compound to induce complete and prolonged remission, with an expected cure rate of 80% to 85%.⁴ The duration of suffering is shortened,

and the amount of scarring is typically reduced. The current study offers subjects with severe acne the opportunity to receive a highly effective treatment with a 2-year follow-up period, during which re-treatment with Absorica® (isotretinoin) or another anti-acne medication will be offered if a relapse occurs.

More than 12 million subjects have been treated with isotretinoin since its approval in 1982.⁴ Side effects include those of the mucocutaneous, musculoskeletal, and ophthalmic systems, as well as headaches and central nervous system effects. Most of the adverse effects are reversible after the drug is discontinued.⁸

Isotretinoin is a known teratogen, with the overall risk of birth defects estimated to be about 30%.⁵ Female subjects of childbearing potential must participate in a risk management program such as iPLEDGE™ to minimize pregnancy risk.

3.0 TRIAL OBJECTIVES AND PURPOSE

3.1 20-Week Active Treatment Period (ATP)

The primary objective during the 20-week ATP of the study will be to investigate the quality of life (QOL) of subjects who are taking Absorica® (isotretinoin) capsules twice daily (bid) without food for the treatment of severe recalcitrant nodular acne.

The secondary objective during the 20-week treatment period will be to investigate the efficacy and safety of Absorica® (isotretinoin) taken bid without food during the ATP.

Safety will be assessed through the monitoring of AEs, laboratory test results, vital signs, and physical examinations.

3.2 104-Week Post-Treatment Period (PTP)

The primary objective during the 104-week PTP of the study is to determine both the time to retreatment and the proportion of subjects who require retreatment with oral isotretinoin during a 2-year PTP.

The secondary objectives during the PTP are:

- To investigate the QOL at the end of the 2-year PTP;
- To investigate the severity of the acne over time, as measured by the Investigator's Global Assessment (IGA) and lesion counts;
- To document any acne treatment (prescription and/or over-the-counter [OTC]) used by those subjects;
- To evaluate the long-term safety during the 2-year PTP.

4.0 STUDY DESIGN

4.1 Overall Study Design

This is a single-arm, open-label study consisting of 2 phases: a 20-week (5-month) open-label ATP and a 104-week (2-year) PTP. The total study duration is to be 124 weeks, excluding a screening period. During the ATP, after a Week 2 visit, visits will be scheduled at 4-week intervals for a total of 8 visits (1 screening visit, 1 baseline visit, and 6 on-study visits). During the PTP, the first visit will be 4 weeks after End of Treatment (EOT), the second visit will be 12 weeks after EOT, and subsequent visits will be scheduled at 26-week (\pm 2 weeks) intervals for a total of 6 visits.

Subjects will provide written informed consent, including mandatory photographic consent, on an informed consent form (ICF). Subjects who are under the age of 18 years will sign an assent form and their parent or guardian will sign the ICF. Subjects will then undergo a complete physical examination and will provide blood samples for hematology and fasting clinical chemistry, including liver function tests and a lipid profile with triglyceride levels. Female subjects of childbearing potential will be required to comply with mandatory pregnancy testing (see [Section 7.4.5](#)) and contraception specifications (see [Section 6.6](#)) before receiving study medication.

Subjects who meet the entry criteria will enter a 20-week ATP, during which they will receive Absorica® (isotretinoin) capsules. Dosing will be at an initial titration dose of approximately 0.5 mg/kg/day divided into 2 daily doses for the first 4 weeks, followed by 16 weeks of dosing with approximately 1 mg/kg/day divided into 2 daily doses. Study medication is to be taken

[figure not shown]
without food (ie, 1 hour before or at least 2 hours after the ingestion of food or beverages other than water).

Beginning at Visit 2 (Baseline) and continuing throughout the ATP and PTP (excluding Visits 3 and 9), subjects will be asked to complete an acne-specific quality of life (acne-QOL) questionnaire and photographs will be taken of the subject's face. Safety during the ATP will be assessed by adverse event (AE) monitoring and laboratory test results. Efficacy will be assessed by lesion counts (nodules, inflammatory lesions) and an IGA.

Subjects who are prescribed a second course of treatment Absorica® or any other formulation of isotretinoin during the PTP will be withdrawn from the study after their lesion count and IGA are recorded. Subjects who use OTC or oral non-isotretinoin acne treatment can remain in the study, but their medication use is to be recorded.

The study design is summarized in [Figure 4-1](#).

Figure 4-1 Study Design

Note: EOT = end of treatment; EOS = end of study

a. A mandatory, confirmatory pregnancy test for female subjects of childbearing potential must be conducted according to the iPLEDGE guidelines.

b. Week 2 safety laboratory tests.

c. 4 Week post treatment safety follow-up

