5.3.1 General Exclusion Criteria

1. Presence of any clinically significant physical examination finding, vital signs measurement, or abnormal laboratory value;
2. Presence of a beard or other facial hair that could interfere with the study assessments;
3. Participated in another clinical trial or received an investigational product within 3 months prior to screening;
4. History of excessive or suspected abuse of alcohol (based on the clinical judgment of the investigator), recreational drugs, and/or drugs of abuse, eg, club drugs, cocaine, ecstasy/MDMA (3,4-methylenedioxymethamphetamine), heroin, inhalants, marijuana, methamphetamine, phencyclidine (PCP), prescription medications, anabolic steroids, etc., which, in the opinion of the investigator, would interfere with participation in the study;
5. Use of prohibited or restricted prior or concomitant medications (see [Section 5.3.5](#)).

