5.3.5 Prohibited Medication Before and/or During the Study

5.3.5.1 Medication Prohibited Before or During the ATP

1. Tegison (etretinate) or Soriatane (acitretin): any previous treatment at any time;
2. Vitamin A supplements: Subjects with known daily intake of >1000 pg for males and >800 pg females will be excluded from the study. During the course of the study, subjects are to limit their intake of vitamin A supplements to <1000 pg for males and <800 pg for females;
3. Systemic corticosteroids (within 30 days prior to Baseline). Very low dose inhaled corticosteroids are allowed;
4. Topical corticosteroids applied to the face within 7 days prior to Baseline;
5. Spironolactone and its derivatives used within 30 days prior to Baseline and during both phases of the study;

6. Phenytoin;
7. Antimicrobials:
 - a. Oral antibiotics or topical antibiotics (on the face) within 14 days of Baseline and throughout the ATP.
 - i. Short courses of antibiotics may be administered during the ATP for purposes other than acne therapy at the discretion of the investigator.
 - ii. (Note: some antibiotics, eg, rifampin and penicillin derivatives, have the potential to decrease the effectiveness of birth control pills. This needs to be taken into consideration by the study investigator).
 - b. Tetracyclines: Isotretinoin use has been associated with a number of cases of pseudotumor cerebri (benign intracranial hypertension), some of which involved concomitant use of tetracyclines. Therefore, concomitant treatment with tetracyclines should be avoided.
 - i. Early signs and symptoms of pseudotumor cerebri include papilledema, headache, nausea and vomiting, and visual disturbances. An ophthalmologist should evaluate subjects for papilledema if these suggestive symptoms develop.
 - ii. Also, if these symptoms occur or if the investigator and/or ophthalmologist judge this to be appropriate, tell the subjects to discontinue isotretinoin immediately and refer them to a neurologist for further evaluation and care. Such cases should be reported to the designated Medical Monitor.
8. Any other medication used to treat acne, including over-the-counter and prescription topical therapies and systemic medications. These should not be used within 14 days of Baseline or during either phase of the study;

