9. Microdose progesterone preparations for contraception in female subjects. The subject must stop using the microdose preparations and switch to an iPLEDGE acceptable form of oral contraceptive under the direction of her primary physician or gynecologist;

Note: Female subjects using combined oral contraceptives are eligible for the study and will be allowed to continue using them if they have been on the contraceptive for at least the last 3 months prior to Screening and there has been no improvement in the status of their acne.
10. Medications that may decrease the effectiveness of birth control products when used concomitantly with hormonal contraceptives. The study investigators are advised to EXERCISE CAUTION and consult the package insert of the medications prior to administering them to females of childbearing ability. Drugs that are known to decrease the effectiveness of hormonal contraceptives should not be used concomitantly with the study medication;
11. Any other medication that the investigator judges to have an adverse effect when given with isotretinoin or any medication disallowed in the protocol;

12. Any physical therapies (ie, PDT, laser, lights, peels, microdermabrasion, etc) within 1 month prior to Baseline and during both phases of the study;
13. Over-the-counter products that may worsen acne, eg, products that contain high iodine levels, such as kelp;
14. Herbal products (St. John's Wort, red clover, milk thistle, etc).

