5.3.5.2 Medication Prohibited During the PTP

1. Tegison (etretinate) or Soriatane (acitretin);
2. Vitamin A supplements: Subjects with known daily intake of >1000 pg for males and >800 pg females will be excluded from the study during both phases of the study (29 months). During the course of the study, subjects are to limit their intake of vitamin A supplements to <1000 pg for males and <800 pg for females;
3. Systemic corticosteroids or topical corticosteroids applied to face. Very low dose inhaled corticosteroids are allowed;
4. Over-the-counter products that may worsen acne, eg, products that contain high iodine levels, such as kelp.
5. Note: During the PTP, any antibiotic therapy given for intercurrent illness (ie, upper respiratory infection, urinary tract infection) must be documented with the name of the antibiotic, dose, and duration of treatment.
6. Note: the contraception methods used by female subjects of childbearing potential during the PTP should be documented.

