6.8 Disallowed Medications

Subjects who had used the following medications at any time are to be excluded from the study:

- Tegison® (etretinate).

- Soriatane® (acitretin).

Use of the following medications, preparations, and treatments is disallowed as noted below.

- 30 days prior to Baseline and throughout the study (both ATP and PTP):
 - Systemic corticosteroids.
 - Spironolactone and its derivatives.
- 14 days prior to Baseline and throughout the study:
 - Antibiotics. Tetracyclines are prohibited during the study. Short courses of other antibiotics can be administered during the study at the discretion of the investigator. [Note: Per [Section 5.3.5](#), antibiotics and tetracyclines are prohibited during ATP but allowed during the PTP]
 - Phenytoin (eg, Dilantin);
 - Any other medication used to treat acne (both ATP and PTP).
- 7 days prior to Baseline:
 - Topical corticosteroids.
- During the study (both ATP and PTP):
 - Vitamin A supplements > 1000 µg for males and >800 µg for females (ATP and PTP)
 - Herbal products (St. John's Wort, red clover, milk thistle, etc).
 - Microdose progesterone preparations (see [Section 6.6](#)).
 - Oral contraceptives with approved anti-acne indication for nodular acne (eg, Ortho Tri-Cyclen®, Yaz®, and Estrostep®). Females using oral contraceptives with anti-acne activity are allowed to continue using them if they had been on the contraceptive for at least the last 3 months prior to screening and there was no improvement in the status of their acne. For subjects who remain on an oral contraceptive during the PTP, it is preferred that they continue on the same medication as in the ATP; if any change is required, it is preferred that the medications named above be avoided. All medications taken should be documented.

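### Sections 6.8 and 5.3.5.1 item 8 prohibit most other acne medication in the post-treatment period, although the same protocol offers it, permits it and measures it in four secondary endpoints

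*Combined protocol and SAP*

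**What the plan says.** Two places prohibit other acne medication after treatment ends.

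- Section 6.8 lists, among items disallowed from 14 days before Baseline onward, "Any other medication used to treat acne (both ATP and PTP").
- Section 5.3.5.1 item 8 covers OTC products, prescription topicals and systemic drugs for acne, and states: "These should not be used within 14 days of Baseline or during either phase of the study". The heading of 5.3.5.1 refers only to the ATP, but the item itself does not stop there.

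One exception is written in. A bracketed note in 6.8 says that "antibiotics and tetracyclines are prohibited during ATP but allowed during the PTP". Section 6.8 also lets women continue an established oral contraceptive with anti-acne activity.

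The rest of the PTP text assumes that acne treatment will occur.

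- Section 2.3 says that isotretinoin or a different acne drug will be made available on relapse.
- Section 3.2 makes recording of prescription and OTC acne treatment a secondary objective.
- Section 4.1: "Subjects who use OTC or oral non-isotretinoin acne treatment can remain in the study, but their medication use is to be recorded".
- Section 4.2.2.2 has four secondary endpoints on non-isotretinoin treatment: the proportion on prescription treatment, the proportion on OTC treatment, the time to either, and acne severity when it starts.
- Section 7.2.7 brings a subject with a flare to an unscheduled visit to discuss treatment.
- Section 5.3.5.2, the PTP's own list of prohibited medication, does not mention other acne medication.

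No sentence says which rule prevails.

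**The concern.** A site cannot follow both sets of instructions. One that uses 6.8 as its medication reference will tell a relapsing subject not to use OTC, topical or other systemic acne treatment. One that works from 2.3, 4.1 and 7.2.7 will offer it.

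The behaviour at issue is itself an outcome. Four secondary endpoints would then partly reflect which section a site reads, not how the acne behaves after treatment. There is a cost to subjects too, because the benefit-risk statement in 2.3 relies on alternatives being available on relapse.

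Section 4.1 also leaves a gap. It names OTC and oral treatment, so users of prescription topicals are not expressly kept in follow-up, although they count towards the prescription endpoint.

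**Working it through.** **Which classes are in conflict**

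| Treatment in the PTP | 6.8 and 5.3.5.1 item 8 | Rest of the protocol |
|---|---|---|
| OTC acne products | Prohibited | Retained and recorded (4.1); endpoint (4.2.2.2) |
| Prescription topicals | Prohibited | Not named in 4.1; counted in 4.2.2.2 |
| Non-antibiotic systemic acne drugs | Prohibited | Oral use retained (4.1); counted in 4.2.2.2 |
| Antibiotics, tetracyclines | Released by the 6.8 note | Consistent |

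The 6.8 note does not separate oral from topical antibiotics, so a topical antibiotic is arguably released as well. The list in 6.8 distinguishes the two phases for antibiotics, yet its acne-medication bullet names the PTP outright. The problem is therefore more than an item placed under the wrong heading in 5.3.5.1.

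**Size: illustration only**

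The plan gives no expected rate of non-isotretinoin treatment and no precision target for these endpoints, so there is no figure to reproduce. Inputs:

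- n = 140, the approximate number of ATP completers in 5.1, taken as PTP entrants; 20 sites (5.1), so 140/20 = 7 per site.
- u = true proportion who would use the treatment: 10%, 20% or 40% (assumed).
- c = share of would-be users who abstain because of the prohibition (assumed). If 2, 5 or 10 of 20 equal-sized sites apply it and all their subjects obey, c = 0.10, 0.25 or 0.50.

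*OTC endpoint.* Measured proportion = u × (1 − c). The 95% half-width at the true rate is h = 1.96 × √(u(1 − u)/140).

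| u | h (points) | c = 0.10 | c = 0.25 | c = 0.50 |
|---|---|---|---|---|
| 10% | 5.0 | 9.0% | 7.5% | 5.0% |
| 20% | 6.6 | 18.0% | 15.0% | 10.0% |
| 40% | 8.1 | 36.0% | 30.0% | 20.0% |

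The shortfall u × c equals h when c = h/u: 4.97/10 = 0.50, 6.63/20 = 0.33 and 8.11/40 = 0.20. In this sketch, between a fifth and a half of would-be users must abstain before the bias matches the sampling error.

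*Prescription endpoint.* Only unreleased classes are suppressed. With s the share of would-be prescription users whose only treatment falls in those classes (assumed), measured = u × (1 − c × s). For u = 20% and c = 0.25, s = 1 gives 15.0% and s = 0.5 gives 20% × (1 − 0.125) = 17.5%. Even with complete obedience (c = 1), s = 0.5 leaves 20% × 0.5 = 10%, not zero.

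*Time to use and severity at use.* Abstention removes or delays first use, so time to use appears longer. Severity at use is then observed in a selected group; the documents do not determine the direction of that bias.

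**The case against.** The strongest reply is that this is a drafting carry-over that sites would see through. The heading of 5.3.5.1 is limited to the ATP, 5.3.5.2 omits the prohibition, and 4.1 states what happens when a subject does use such treatment. On this view use is discouraged but tolerated, and it is captured regardless, because 6.5, 7.2.7 and Table 1-2 record medication whether or not it is allowed.

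Much of this stands. The balance of PTP text favours use and retention, nothing shows that a PTP prohibition was intended, and total suppression is unlikely. But recording cannot recover use that a site discouraged, and tolerating use is not the offer made in 2.3. Section 6.8 also names the PTP expressly.

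It is fair, too, that the magnitude rests on assumed behaviour. With 5 of 20 sites applying the rule, shortfalls of 2.5 and 5 points lie inside half-widths of 5.0 and 6.6; only at 40% use does the shortfall (10 points) exceed the half-width (8.1). With 2 sites none does.

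A reader might infer two stronger points that the documents do not support.

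- *That all acne medication is prohibited, so obedience would yield zero use by rule.* The antibiotic note and the contraceptive provision defeat this for the prescription endpoint.
- *That the primary PTP endpoint, retreatment with isotretinoin, is biased because users of prohibited medication are withdrawn.* No rule requires them to leave; among acne treatments only isotretinoin mandates withdrawal (4.1, 7.2.8). Item 5 of 5.3.1 ("Use of prohibited or restricted prior or concomitant medications") is an entry criterion, and Table 1-1 schedules eligibility review at Visits 1 and 2 only; Table 1-2 has no such row. Withdrawal for non-adherence under 5.4 is discretionary and, for OTC and oral users, would run against 4.1. Even the direction is open: withdrawal could hide later retreatment, while denying alternatives could push relapsing subjects to isotretinoin.

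**Conclusion.** The point holds as an internal inconsistency: the plan is wrong as written. Sections 6.8 and 5.3.5.1 item 8 prohibit, in the PTP, OTC, prescription topical and non-antibiotic systemic acne treatment that 2.3, 3.2, 4.2.2.2 and 7.2.7 assume will be offered, recorded or measured. Section 4.1 keeps OTC and oral users in the study, and 5.3.5.2 does not repeat the prohibition.

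Wherever sites enforce the rule, the two use proportions are biased downward, and time to use and severity at use are distorted. The size cannot be derived from the documents: it depends on true use, on how many sites apply the rule and on how far subjects obey, all of which are assumed above. The consequence is confined to descriptive secondary estimates. Section 8.2 plans no hypothesis tests, so no error rate is affected, and no effect on the primary PTP endpoint is established.

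**What to change.** - **5.3.5.1 item 8:** limit the period to the 14 days before Baseline and the ATP.
- **6.8, acne-medication bullet:** state that it applies before Baseline and during the ATP only. Deleting the parenthesis alone is not enough, because the bullet sits under a line that runs throughout the study.
- **4.1:** state that a subject who starts any non-isotretinoin acne treatment not otherwise prohibited in the PTP, whether OTC or prescription, topical or oral, stays in follow-up and has the use recorded. This closes the gap on prescription topicals.

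The phrase *not otherwise prohibited* leaves the specific PTP restrictions in place, such as those on spironolactone and physical therapies (5.3.5.1 items 5 and 12) and on acitretin, etretinate and corticosteroids (5.3.5.2). Withdrawal for medical reasons under 5.4 is unchanged.

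The cost is a short amendment and a clarification to sites. No visit or data item is added, since Table 1-2 already schedules a medication review at all six PTP visits.
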